• If subjects who do not have the capacity to give legally effective consent are included, describe how diminished capacity will be assessed. Will a periodic reassessment occur? If so, when? Will the subject be consented if the decisional capacity improves?

Clinic nurses will assess the participant's capacity to provide consent prior to referring them to the study. Patients who lack the intellectual capacity to give legally effective consent, who are medically unstable, or who are in acute psychiatric distress, will not be enrolled and will instead be referred for appropriate care within the clinics. These participants will be screened for capacity again at their next HIV appointment, and will have the opportunity to enroll at that time if their decisional capacity has improved.

Study Interventions

• If not already presented in #4 above, describe study-related treatment or use of an investigational drug or biologic (with dosages), or device, or use of another form of intervention (i.e., either physical procedures or manipulation of the subject or the subject's environment) for research purposes.

Risk/Benefit Assessment

Include a thorough description of how risks and discomforts will be minimized (per 45 CFR 46.111(a) (1 and 2)). Consider physical, psychological, legal, economic and social risks as applicable. If vulnerable populations are to be included (such as children, pregnant individuals, imprisoned persons or cognitively impaired adults), what special precautions will be used to minimize risks to these subjects? Also identify what available alternatives the person has if he/she chooses not to participate in the study. Describe the possible benefits to the subject. What is the importance of the knowledge expected to result from the research?

Ethical considerations for the study will be grounded in recent NIMH guidance on Conducting Research with Participants at Elevated Risk for Suicide. All participants will provide written informed consent prior to participation and a decision not to participate will in no way influence the patient's eligibility for standard care at the clinic. We will continually monitor safety indicators, including suicide attempts and suicide deaths. In the unlikely event of (a) increases in suicidal behavior or (b) greater suicidality in the intervention condition as compared to control, the trial will be discontinued.

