 Describe endpoints and power calculations. Provide a detailed description of how study data will be analyzed, including statistical methods used, and how ineligible subjects will be handled and which subjects will be included for analysis. Include planned sample size justification. Provide estimated time to target accrual and accrual rate. Describe interim analysis including plans to stop accrual during monitoring. Phase I studies, include dose escalation schema and criteria for dose escalation with definition of MTD and DLT.

Qualitative data will be analyzed using a thematic approach based on grounded theory and the constant comparative method, a rigorous set of inductive procedures to identify and examine themes from textual data in a way that is transparent and reproducible. Interview transcripts will first be summarized in a qualitative memo, including representative quotes, and organized around a priori domains reflecting the components of the interview guides and CFIR. Next, the memos will be uploaded to NVivo software for coding. Within the broader domains, emerging themes from the interviews will be identified and added to a codebook to develop a coding structure. Each memo will be coded by 2 team members, inter-coder agreement will be calculated, and disagreements will be reconciled via consensus discussion with a 3rd team member. After coding, we will produce NVivo queries and analytic memos to synthesize content, compare participant characteristics, and draw deeper meaning on themes. Qualitative results will be synthesized with the input of the Tanzanian research team, developed into at least one research manuscript, and submitted for publication.

Scale validation will include evaluation of internal consistency of each instrument (Cronbach's alpha and item-scale correlation), convergent validity among related measures, and confirmatory factor analysis to assess whether the factor structure of the English version of manuscript is retained in the Tanzaniain clinical sample.

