Feasibility and acceptability of the intervention will be described by retention patterns, participant satisfaction, fidelity, and implementation cost. *Participant satisfaction* will be measured using the Client Satisfaction Questionnaire⁹³ at the 3-month survey and defined as a mean score \geq 3 on a 1-4 scale. *Fidelit y* to the manual will be measured by TQS and deemed acceptable if mean scores are \geq 3 on a 0-4 scale. *Co st* of the intervention will be tracked, including the time for training, supervision, and actual costs incurred.

Potential efficacy will be assessed by analyzing differences by condition in primary outcomes (suicidality, HIV care engagement, viral load) and secondary outcomes (depression, social support, quality of life). The trial will not be powered to detect significant intervention effects or stable effect sizes; however, we will conduct these analyses to examine the potential for effects in a larger trial. Mixed-effects regression will be used to model pre-post differences within and between arms using a time by condition model specification (time, condition, and time*condition). Individual-level random intercepts will be used to account for correlation due to repeated measurement. This mixed-effects regression approach allows us to control for baseline outcome values that may not be balanced between groups due to small sample size, and may improve precision of treatment effect estimates. We will also generate parameter estimates and ranges of values to estimate power for a future larger clinical trial study.

Data & Safety Monitoring

• Summarize safety concerns, and describe the methods to monitor research subjects and their data to ensure their safety, including who will monitor the data, and the frequency of such monitoring. If a data monitoring committee will be used, describe its operation, including stopping rules and frequency of review, and if it is independent of the sponsor (per 45 CFR 46.111(a) (6)).

The Duke PI [name] will receive guidance on research with patients at-risk of suicide in monthly mentoring meetings with [name], a recognized expert in the field of suicide prevention research. During these meetings, Drs. [name] and [name] will review safety data from the study, including trends in suicidal ideation and any reported instances of suicidal behavior or death by suicide

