among participants. In the unlikely event of (a) increases in suicidal behavior from baseline to follow-up survey or (b) greater suicidality in the intervention condition as compared to control as measured in the follow-up survey, the trial will be discontinued.

Participants identified to be in acute crisis at any of the research sites will be referred to [name] or [name] at the psychiatry service at KCMC, or to mental health staff at Majengo Health Centre or Mawenzi Hospital, in a safe and timely manner. Study research assistants (RAs) and nurse interventionists will be trained in suicide risk assessment using a manual developed by the U.S. Department of Veteran Affairs (2013). This framework incorporates considerations of whether the person has a plan to commit suicide, intent to carry out the plan, access to the means to carry out the plan, or a history of suicidal behavior. Risk assessment will be conducted in each intervention session and whenever emotional distress is communicated outside of sessions (e.g., during weekly text message check-ins).

"Acute crisis" will be defined as a participant meeting more than one of these criteria (plan, intent, means, history). In the event of an acute crisis assessed by a study RA, we will immediately initiate a contact with a psychiatric nurse. If the acute crisis is assessed by a psychiatric nurse, we will notify the consulting psychiatrist ([name] or [name]). Counseling will be provided, and study staff will maintain contact with the participant until a plan has been made to protect the participant's safety, which may include accompanying them to the psychiatric unit at KCMC or Mawenzi Hospital or contacting a family member or friend to stay with the patient and provide support. If the consulting psychiatrist determines that a participant is able to return home with a family member or friend, a drop in session will be scheduled for the next day to reevaluate risk and progress.

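### The mandatory stopping rule acts on bare direction with no measure, margin or number of looks, so at one look it stops a harmless pilot up to about half the time, depending on the measure

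*Combined protocol and SAP*

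**What the plan says.** The rule appears twice in the combined protocol and SAP.

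- **Data & Safety Monitoring:** "In the unlikely event of (a) increases in suicidal behavior from baseline to follow-up survey or (b) greater suicidality in the intervention condition". The sentence goes on to tie the second trigger to the follow-up survey and to make the consequence automatic: "greater suicidality in the intervention condition as compared to control as measured in the follow-up survey, the trial will be discontinued".
- **Risk/Benefit Assessment:** "In the unlikely event of (a) increases in suicidal behavior or (b) greater suicidality in the intervention condition as compared to control", with the same consequence but no reference to any survey. The sentence before it reads "We will continually monitor safety indicators, including suicide attempts and suicide deaths".

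The Data & Safety Monitoring section places the rule within monthly meetings at which the principal investigator and a suicide-prevention expert "will review safety data from the study, including trends in suicidal ideation and any reported instances of suicidal behavior or death by suicide".

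The Data Analysis & Statistical Considerations section lists suicidality first among the primary outcomes. It also says: "The trial will not be powered to detect significant intervention effects or stable effect sizes". Design & Procedures gives 60 participants, 30 per arm. All have had suicidal ideation in the past month, and the control arm receives an active safety-planning session.

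**The concern.** Trigger (a) is any increase in suicidal behavior. Trigger (b) is any excess of suicidality in the intervention arm. Neither has a threshold, and the consequence is mandatory. Followed to the letter, trigger (b) stops the trial on the sign of a difference in a primary outcome, in a study whose own plan says it cannot estimate that difference stably.

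Two things are at stake. If the rule is followed, a harmless intervention can be discontinued by chance, and readers would take the stop as a harm signal. If the team sees a trivial excess and carries on, it has departed from its written safety rule after seeing the data. Either is awkward to defend, and both can be avoided by wording agreed beforehand.

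**Working it through.** The documents give no stopping probability, error rate, SD or event rate for this rule, so there is no stated figure to reproduce. The check asks how often the literal rule fires.

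**Inputs from the documents.** 30 per arm (Design & Procedures, assignment to condition). Triggers (a) and (b) as worded in Data & Safety Monitoring. The C-SSRS has 6 items (Selection of Subjects).

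**Assumptions.** One look with all 30 per arm. Any numerical excess counts. Binary event rates and effect sizes are assumed and shown as ranges.

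**1. Trigger (b), mean score.** The SE of the arm difference is sqrt(2/30) = 0.258 SD. With true benefit d, P(fires) = Φ(−d/0.258).

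| True benefit | d/SE | P(fires) |
|---|---|---|
| none | 0 | 50% |
| 0.2 SD | 0.77 | 22% |
| 0.3 SD | 1.16 | 12% |
| 0.5 SD | 1.94 | 2.6% |

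The 50% follows from symmetry and does not depend on the sample size or SD. Ties lower it slightly. For an integer 0-6 score, exact convolution gives tie probabilities of 2.6% (uniform), 3.4% (skewed) and 5.1% (80% at zero). Then (1 − P(tie))/2 = 48.7%, 48.3% and 47.5%.

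**2. Trigger (b), binary measure, no true difference.** P(fires) = (1 − P(tie))/2, with P(tie) from two independent Binomial(30, p) counts. For example, at p = 1%, P(tie) = 0.5985 and (1 − 0.5985)/2 = 20%.

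| Assumed rate | P(fires) |
|---|---|
| 0.5% | 12% |
| 1% | 20% |
| 2% | 29% |
| 5% | 38% |
| 10% | 41% |
| 20% | 44% |
| 50% | 45% |

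The probability falls below 10% only at a rate under about 0.39%, which is 60 × 0.0039 = 0.23 expected events in the whole trial.

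**3. Triggers (a) or (b), both scored on suicidal behavior.** The baseline count is Binomial(60, p0). The follow-up counts are Binomial(30, p1) in each arm. Baseline is taken as independent of follow-up. The rule fires if the follow-up total exceeds the baseline total, or if the intervention count exceeds the control count (exact enumeration).

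| Baseline → follow-up rate | (a) alone | (b) alone | either |
|---|---|---|---|
| 2% → 2% | 36% | 29% | 51% |
| 5% → 5% | 41% | 38% | 63% |
| 10% → 10% | 44% | 41% | 67% |
| 10% → 5% | 11% | 38% | 44% |

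In simulation, a within-person latent correlation of 0.5 moves the three stable-rate totals only to 50%, 62% and 66%.

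**4. What the sensitivity buys.** At one look with 30 per arm, trigger (b) detects a 0.5 SD harm on a mean score with probability Φ(1.94) = 97%. If the intervention doubles a binary rate of 2%, 5% or 10%, it fires 51%, 69% or 82% of the time.

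**The case against.** The strongest reply is that unlikely is a forecast, not an error rate. Purpose of the Study hypothesises reduced ideation and no added risk of suicidal behavior, and under such a benefit trigger (b) on a mean score is much less likely to fire (12% at 0.3 SD, 2.6% at 0.5 SD). This stands. A reader might infer from the 50% that the word is simply wrong, but the documents do not support that. What they lack is any statement of the benefit the forecast relies on, and that benefit must be over an active control.

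Second, the rule sits within expert review of trends and reported events, so judgment may be intended, and operational detail may be meant for the detailed study protocol planned under Aim 2. Both are possible. As written, though, the consequence is automatic.

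Third, trigger (b) waits for the follow-up survey. The only survey time named is 3 months, when the three sessions at two-week intervals would normally be over. At full follow-up little is left to stop. This also stands and limits the practical cost.

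Other stronger readings should be resisted:

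- **Repeated looks.** A reader might multiply the false stops by the monthly meetings. Repeated between-arm comparisons would raise them, but no schedule for trigger (b) is stated, so no figure is claimed.
- **Contradiction.** The two statements differ in scope, but the shorter can be read as a summary of the longer. Trigger (a) might cover a death under either.
- **Participants left exposed.** The rule errs toward stopping, and individual risk is handled by separate referral and crisis procedures. That does not make the rule sensitive to rare events, as the 51% for a doubling from 2% shows.

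**Conclusion.** The concern holds as a defect in the rule as written, and it should be fixed. At one look with 30 per arm and no true difference, literal trigger (b) fires 50% of the time on a mean score, about 47-49% on an integer 0-6 score, and 20-45% on a binary measure at rates of 1-50%. With trigger (a) added on suicidal behavior, the rule fires 51-67% of the time at a stable rate of 2-10%, and 44% if the rate halves from 10% to 5%. These results rest on the literal reading, complete data, assumed rates and, for the combined figures, independence of baseline and follow-up.

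Unlikely holds only if a sizeable benefit over the active control is assumed, or if the measure is a very rare event. Because every participant enters with recent ideation, a very rare event is plausible if suicidality means attempts or deaths. It is hard to assume if suicidality means any positive C-SSRS item. The scope difference between the two sections is real but secondary.

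**What to change.** Reconcile the statements in Risk/Benefit Assessment and Data & Safety Monitoring into one rule that gives:

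- the measure, for example whether it is the C-SSRS, which Design & Procedures and Risk/Benefit Assessment already have re-administered at the end of counseling calls in both arms;
- the timing, the minimum data and the number of reviews;
- whether attempts and deaths reported outside the survey count toward a trigger;
- the between-arm criterion, or a plain statement that reviewers judge, at a level chosen by the sponsor and its safety reviewers.

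Report the probability of stopping under no difference and under the hypothesised benefit, and the chance of detecting harm. Delete unlikely or support it with those figures. If a deliberately sensitive rule is wanted, say so and give its false-stop rate.

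The cost is protocol wording and a short table from the existing statistical support, with no added participants or visits. The downside is that any criterion stricter than bare direction lowers sensitivity to real harm, and that loss should be stated beside the gain.
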